The projected sample size is 24 subjects. Our current estimates indicate that the confidence interval for studies of 21 individuals with pain intensity ratings will determine the pharmacodynamic parameters with a corrected confidence range < 20%. A corrected confidence range < 20% implies that mixed effect analysis will distinguish covariate effects in the range of 40% in a study with 21 or more subjects. This is the range at which the covariate effect may be clinically consequential. In practice, mixed-effects analysis with NONMEM is often sensitive to covariate effects smaller than predicted by preliminary analyses. The sample size is increased to 24 to provide stratification by age (3 strata), weight (2 strata), and sex. The crossover design permits accurate determination of dose linearity despite expected high inter-subject variability in pain ratings.

Interventions and Interactions

At all study visits temperature will be measured and participants queried regarding recent history of symptoms commonly associated with COVID-19 or recent close contacts with anyone with a positive COVID-19 test.

Study Visit 1:

The participant will report to the Pain CRU or the Wake Forest CTSI CRU. The participant will review and sign the Informed Consent. After informed consent is adequately

obtained, a detailed medical history will be obtained from the participant, female participants will have a urine pregnancy test performed to determine pregnancy status. Vital signs to include blood pressure (BP), heart rate (HR), respiratory rate (Resp) and oxyhemoglobin saturation by pulse oximetry (POX) will be measured and recorded along with height and weight.

Once eligibility has been determined the participant will be trained in study procedures. This will include pain ratings to brief (5 sec) heat stimuli on the lateral calf to 39, 41, 43, 45, 47, and 49°C and then a pain intensity rating each minute for 5 mins during heating to 45°C. If the pain report to 45°C is < 2 at the end of the 5 min, a second trial using 46°C will be done, and if that also results in pain intensity < 2, a third trial with 47°C will be performed. Subjects who have pain intensity < 1 with the 47°C 5-min stimulus will not be further studied. The duration for visit 2 will be approximately 2 hours

Study Visit 2

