desaturation (< 90) will be treated with supplemental oxygen, nasal cannula, face mask, or non-rebreathing mask depending upon the degree desaturation and the response to therapy.

Outcome Measure(s)

Primary Outcome Measure

Name: Verbal pain score (0-10) at the end of 5 min of skin heating

Type: Primary

Time Frame: For 45 minutes after the end of each study drug infusion

Description: Pain scores are measured each minute during 5 min heating of the skin of the calf

Analytical Plan

The primary analysis will use NONMEM to create a dose response at the time of peak oxytocin effect on pain at the end of a 5 min noxious heat stimulus. To do so, pain scores over time will first be modeled using NONMEM with derived parameters of maximum effect (Emax), predicted concentrations from the PK/PD model to produce a 50% and 90% maximum drug effect (C50 and C90, respectively), the steepness of the dose response curve (γ), and the time to peak effect. Inter-subject variability (e.g., biological variability) will evaluate additive, proportional, and exponential models. Residual intrasubject variability (e.g., noise) will typically require an additive and multiplicative error model. The influence of covariates (e.g., age, sex, weight) on model parameters will be analyzed by serial inclusion / exclusion, with significance determined by the likelihood ratio test ($p < 0.01$ if the decrease in $-2 \log$ likelihood exceeds 6.6 ($\chi^2_{0.99}$, $df = 1$)). Parameters will be estimated using first-order conditional estimate with η - ε interaction.

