Covariate effects deemed significant by likelihood ratio test will be validated using jackknife cross-validation [10]. Jackknife cross-validation provides an estimate of the utility of the covariate to inform the pharmacodynamics in a future individual, rather than merely characterize the pharmacodynamics in the individuals from which the model was derived. The jackknife cross-validation divides the data into N subsets. Each subset leaves out a single individual. The parameters of the model are re-estimated for each subset with and without the covariate being validated. The inaccuracy (mean $((|measured - predicted|) / predicted)$), of the model with and without the covariate is measured in the excluded individual. The covariate is only being included in the final model if the improvement in model accuracy in the N iterations is significantly greater than 0. Jackknife cross-validation helps compensate for NONMEM's ability to identify very small covariate effects that do not meaningfully contribute to accuracy in future patients.

Expected outcomes. Based on pain ratings and an estimate of the PK/PD model from preliminary data (Fig 1), we anticipate that the maximum oxytocin effect is a 50-60% reduction in pain rating from the 5 min heat stimulus. We anticipate that the oxytocin dose range will demonstrate a sigmoidal dose-response with a peak within 10 min after the end of infusion and an ED80 of ~ 5 μ g. In a separate simulation of 7 μ g oxytocin without a prior injection of 0.3 μ g, the peak effect was within 1% of the same value, supporting this stepped dosing study design. The expected peak plasma oxytocin concentration after the 7 μ g infusion following the 0.3 μ g infusion is 400 pg/ml, below that which produced subjective symptoms in previous studies.

Human Subjects Protection

Subject Recruitment Methods

Healthy subjects will be recruited from our current database of volunteers BG05-468, word of mouth and Be Involved website; The research nurses; [name] and [name], LPN will conduct the recruitment of study subjects.

Potential subjects from the database will be contacted via phone or email, per their request. Potential subjects from the Be Involved website will be contacted according to the information they provide.

Informed Consent

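### The jackknife accuracy gain is presented as a covariate's utility in a future individual, but the covariate is first selected on all subjects, so the estimated gain is optimistic for weak or null effects

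*Combined protocol and SAP*

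**What the plan says.** The Analytical Plan describes two consecutive steps.

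- **Screen.** "The influence of covariates (e.g., age, sex, weight) on model parameters will be analyzed by serial inclusion / exclusion", with a covariate counted as significant when the drop in -2 log "likelihood exceeds 6.6" (p < 0.01, 1 df). No subset of subjects is mentioned, so the natural reading is that all subjects are used.
- **Validation.** "Covariate effects deemed significant by likelihood ratio test will be validated using jackknife cross-validation". For the subsets, "Each subset leaves out a single individual", and then "The parameters of the model are re-estimated for each subset with and without the covariate being validated".

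The purpose is stated directly: the jackknife "provides an estimate of the utility of the covariate to inform the pharmacodynamics in a future individual". The plan contrasts this with describing only the people from whom the model was built. The gain has one stated use: a covariate enters the final model only if its accuracy improvement is significantly above zero. The test, its level and its sidedness are not given. The Sample Size section states: "The projected sample size is 24 subjects". Sex and age effects are the first additional objective.

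**The concern.** A left-out subject stands in for a future individual only if that subject played no part in building the model being tested. Here the covariate is fixed before the first leave-one-out run, by a screen that used every subject. Each run repeats the estimation but not the choice. A covariate that passed by chance did so because of a pattern in these same subjects, and removing one of them leaves that pattern almost intact.

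The gain in the inclusion rule is therefore higher on average than the gain a new subject would receive. At stake is what the jackknife can be said to show about sex, age or weight. The plan gives no other basis for calling a covariate useful in future patients, and it mentions no nested selection, external data or correction for selection.

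**Working it through.** **Inputs from the documents.** N = 24; age, sex and weight as example covariates, tested on several model parameters (the number of covariate-parameter pairs is not stated); threshold 6.6; leave-one-subject-out; inaccuracy = mean of |measured - predicted| / predicted.

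**Assumptions, not in the documents.** One value per subject replaces the NONMEM model, with mean 5 and residual SD 1 (20% coefficient of variation). There are 3 or 12 independent, normally distributed candidates, and the one with the largest statistic is kept if it passes. The true effect is 0, 0.3, 0.5 or 0.8 residual SD per SD of covariate. The jackknife test is a one-sided t-test at 5% on the 24 gains.

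**Step 1: the plan's own figure.** The 0.99 quantile of chi-square with 1 df is 6.635, and the tail probability at 6.6 is 0.0102. The threshold is reproduced apart from rounding.

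**Step 2: what passing the screen implies.** In the surrogate the statistic is -N ln(1 - r²). Exceeding 6.6 with N = 24 requires r² > 1 - exp(-6.6/24) = 0.240, so |r| > 0.49. Every covariate reaching the jackknife, including pure noise, has at least that correlation in the same 24 subjects.

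**Step 3: three versions of the gain** (inaccuracy without minus with the covariate, in percentage points, averaged over data sets in which a covariate passed).

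- *Apparent*: the plan's procedure, with the covariate fixed and parameters re-estimated on 23.
- *Repeated screen*: the covariate is re-selected on the 23, or none is used if none passes.
- *True*: the gain in 4,000 new subjects.

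There were 12,000 runs for effects 0 and 0.3, and 4,000 for 0.5 and 0.8.

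| Candidates | Effect (SD) | Some covariate passes | Apparent | Repeated screen | True |
|---|---|---|---|---|---|
| 3 | 0 | 4.0% | +1.9 | 0.0 | -2.7 |
| 3 | 0.3 | 16.7% | +2.2 | +0.5 | -1.1 |
| 3 | 0.5 | 43.7% | +2.7 | +1.5 | +1.0 |
| 3 | 0.8 | 83.9% | +4.1 | +3.6 | +3.5 |
| 12 | 0 | 16.5% | +1.8 | -0.4 | -2.9 |
| 12 | 0.3 | 26.8% | +2.1 | 0.0 | -1.8 |
| 12 | 0.5 | 50.5% | +2.7 | +1.0 | 0.0 |

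The case of 12 candidates with a 0.8 SD effect was not completed. With 3 candidates, apparent minus true is 1.9 + 2.7 = 4.6, 2.2 + 1.1 = 3.3, 2.7 - 1.0 = 1.7 and 4.1 - 3.5 = 0.6 points. For scale, inaccuracy without a covariate in the null case is about √(2/π) × 20 = 16 points. When a noise covariate passed the screen, the apparent gain was positive in about 95% of data sets.

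**Step 4: control.** For one pre-specified covariate with no screen, apparent and true gain agree: -0.45 against -0.39 (no effect) and +1.30 against +1.37 (0.5 SD). The optimism comes from full-data selection, not from leaving one out.

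**Step 5: inclusion decisions.** Of null covariates that passed the screen, 12.3% (3 candidates) and 12.7% (12 candidates) also passed the jackknife test. Over all null trials that is 4.0% × 12.3% = 0.5% and 16.5% × 12.7% = 2.1%, well below the screen alone. With the screen repeated, about 8% of screened-in null covariates pass, or 4.0% × 8% = 0.3% of null trials with 3 candidates.

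**Step 6: a different surrogate** (log scale, plain absolute error, candidates sex, age and weight; gains as a percentage of mean absolute error). A screened-in null covariate had apparent +12%, repeated screen -1%, true -13%. A true 40% sex effect gave +15%, +8% and +3% with an assumed between-subject log SD of 0.45, and +18%, +13% and +11% with 0.30. In a re-run of the null case with log SD 0.45, apparent and true gains were +12% and -14%. Adding residual noise with an SD equal to, then twice, the between-subject SD shrank these to +6% and -8%, then +3% and -3%. The direction held, but the size did not.

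**The case against.** The best defence is that the plan treats the jackknife as a gate, not as a result to publish. As a gate it works: with 3 candidates it cuts false inclusions from 4.0% to 0.5% of null trials. That serves the plan's stated aim of holding back trivial covariate effects. Repeating the screen would change this only to about 0.3%.

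The repeated screen is not unbiased either. It gives 0.0 against a true -2.7 for a null effect, and +0.5 against -1.1 at 0.3 SD. It measures a selection procedure, not a single covariate. If runs select different covariates, the plan's per-covariate rule no longer applies as written. The sizes also come from surrogates simpler than repeated pain ratings with additive and multiplicative error, and residual noise shrinks them.

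All of this stands, and it limits the consequence. A reader might infer that the trial will publish inflated sex or age benefits. The documents do not support that, because nowhere do they promise to report the gain. A reader might also infer that false covariates will flood the final model; Step 5 shows the reverse.

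The defence does not answer the mismatch between stated purpose and procedure. The plan says the jackknife speaks to someone outside the modelled group, yet every left-out subject helped choose the covariate.

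**Conclusion.** The point holds in a limited form. For covariates that passed the screen, the estimated gain in the inclusion rule is optimistic as a statement about a future individual. Under the 20% variability assumption with 3 candidates, the optimism is about 4.6 points for a null effect and 3.3 at 0.3 SD, with the wrong sign on average in both cases. It falls to 1.7 points at 0.5 SD and 0.6 at 0.8 SD. The direction was the same in every scenario run. The sizes depend on the surrogate, the assumed variability and the number of candidates, none of which the documents settle.

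The effect on inclusion decisions is small. It would be tempting to conclude that the dose-response result is compromised, but the documents do not support this: covariate effects are an additional objective, and the main one is not directly affected. It would also be wrong to expect nested selection to deliver an unbiased gain; it reduces the optimism without removing it.

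**What to change.** In the Analytical Plan:

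1. In each leave-one-out run, repeat the whole serial inclusion/exclusion step on the remaining N - 1 subjects. Predict the left-out subject with the model that run selects (no covariate if none is selected), and compute the gain from those errors.
2. For a per-covariate decision, credit a covariate only in runs that re-select it and count a gain of zero in the others.
3. Report the share of runs that re-select each covariate.
4. Describe the nested gain as the performance of the selection procedure, with optimism reduced but not removed.
5. State the number of covariate-parameter pairs searched, and the test, level and sidedness used to judge whether the gain exceeds zero.

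If the search is not repeated, reword the jackknife paragraph so that the gain is conditional on selection in the full data and is not offered as an estimate for a future individual.

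The cost is about 24 extra covariate searches, a few sentences of text and smaller estimated gains. The rewording alone needs no computation. No change to the design or data collection is needed.

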Signed informed consent will be obtained from each subject. [name] or [name], LPN will obtain consent. Potential subjects will be consented in the CRU. A private room will be utilized during the consent process and all study visits.

Confidentiality and Privacy

Confidentiality will be protected by collecting only information needed to assess study outcomes, minimizing to the fullest extent possible the collection of any information that could directly identify subjects, and maintaining all study information in a secure manner. To help ensure subject privacy and confidentiality, only a unique study identifier will appear on the data collection form. Any collected patient identifying information corresponding to the unique study identifier will be maintained on a linkage file, stored separately from the data. The linkage file will be kept secure, with access limited to designated study personnel. Following data collection subject identifying information will be destroyed 3 years after closure of the study, in confidential shredding disposal bins consistent with data validation and study design, producing an anonymous analytical data set. Data access will be limited to study staff. Data and records will be kept locked and secured, with any computer data password protected. No reference to any individual participant will appear in reports, presentations, or publications that may arise from the study.

Data and Safety Monitoring

The principal investigator will be responsible for the overall monitoring of the data and safety of study participants. The principal investigator will be assisted by other members of the study staff.

The DSMP outlined below will provide appropriate oversight and monitoring to ensure the safety of participants, the validity of the data, and make intermittent recommendations whether to continue, modify or stop the study. The DSMP will utilize an independent DSMB to ensure the effective institution of the DSMP.

This DSMB will have discretion to unblind any results, or conduct any inquiry needed to ensure the safety and efficacy of the trial at the request of the DSMB chair. The committee will maintain a written record of its meetings.

Scope of Data Monitoring

The primary source of the data will be adverse event reporting.

Study admission data

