Monitoring of admission data will include the number of subjects requesting participation in the study, number of subjects screened and number of subjects admitted to the study. The DSMB may request a report of the reason why subjects were disqualified from participating in the study. For subjects admitted to the study, the DSMB will review eligibility criteria for admitted subject, any protocol deviations and/or violations, and the demographic distribution of the subjects by group.

Protocol Compliance

The DSMB will monitor the data to assess compliance with the protocols including the adherence to the randomization schedule. The DSMB will also monitor the quality and completeness of the data being collected, including the frequency of missing or erroneous data, and presence and frequency of outliers.

Safety Data

Monitoring of safety data will include review of Adverse Events (AEs) and Serious Adverse Events (SAEs), trial retention, and reason for drop out. Safety information will be reported to the DSMB in an unblinded manner. Formal statistical analyses of the safety data may be requested by the DSMB. For SAEs, data will include all the adverse event data meeting the FDA definition of serious adverse events. In the assessment of SAEs, the DSMB will review each individual case including treatment group assignment. After each meeting of the DSMB, the secretary will forward a summary report of all serious and unexpected adverse experiences to the principal investigator to summarize the DSMB's review of the serious and unexpected adverse events reported. Furthermore, the DSMB will make a recommendation to continue, modify or halt the study protocol. This report will be transmitted to the Wake Forest University IRB and NIH. Safety data will be prepared for review following the enrollment of each 24 subjects.

Establishing a DSMB Board membership

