The DSMB will be appointed by [name] and [name] with the purpose of reviewing, approval, and monitoring the implementation of the DSMP. The DSMB will have two members encompassing multidisciplinary expertise who are not involved in the study protocol. Board members will have no financial and/or scientific ties to the outcome of the clinical trials to avoid any real or perceived conflict of interest. The DSMB will include the following physicians; [name]., Associate Professor of Anesthesiology and Director of Obstetric and Gynecologic Anesthesiology and [name]., Associate Professor and Vice Chair for Research in Anesthesiology, Wake Forest School of Medicine.

Board meeting schedule

The board will have scheduled meetings twice a year and expedited meetings to review unexpected SAEs or other urgent issues that may arise during the trial. Unscheduled meetings may be initiated by the DSMB chair, [name], or [name]. The data to be reviewed by the DSMB will be available to the Board members.

DSMB Recommendations:

DSMB recommendations will be made in writing by The DSMB chair to [name]. The secretary will prepare meeting minutes for inclusion in the DSMB report. The draft report will be reviewed by all Board members prior to issuance of the final report. DSMB recommendations will then be forwarded to the NINDS program officer and Wake Forest University IRB.

Volunteer Payment

Participants will be paid a total of \$400 according to the following payment schedule which we have used throughout the last 10 years. We believe that this payment schedule is fair and appropriate, paying for each procedure attempted and an additional payment for completion of the entire study.

Completion of study visit 1: \$50

Study visit 2: placement of IV-\$25, IV infusion and thermal testing-\$100

Study visit 3: placement of IV-\$25, IV infusion and thermal testing-\$100

Completion of all study related procedures: \$100

If an IV cannot be placed on Study visit 2: subject will be compensated \$50 and subject replaced

Long-term Follow-up

Volunteers will be contacted daily within the following week and questioned about adverse events from the study.

Reporting of Unanticipated Problems, Adverse Events or Deviations

Any unanticipated problems, serious and unexpected adverse events, deviations or protocol changes will be promptly reported by the principal investigator or designated member of the research team to the IRB, DSMC and the FDA if appropriate.

References

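### DSMB safety data are to be prepared after each 24 subjects enrolled in a trial of 24, so this trigger gives one package at about the end of enrolment and none before

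*Combined protocol and SAP*

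**What the plan says.** The Safety Data section, within the data and safety monitoring plan, gives one timing for compiling data: "Safety data will be prepared for review following the enrollment of each 24 subjects". The Sample Size section states: "The projected sample size is 24 subjects". The opening of Data and Safety Monitoring says that the plan is meant to "make intermittent recommendations whether to continue, modify or stop the study".

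Other text also bears on what the board sees:

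- **Content.** The Safety Data section covers non-serious as well as serious adverse events, and adds: "Safety information will be reported to the DSMB in an unblinded manner".
- **Meetings.** Under Board meeting schedule: "The board will have scheduled meetings twice a year and expedited meetings to review unexpected SAEs" or other urgent matters. Also: "Unscheduled meetings may be initiated by the DSMB chair" or by two other named people.
- **Output.** According to the Safety Data section, a summary of serious and unexpected events goes to the principal investigator after each meeting. The board also recommends whether to continue, modify or halt.
- **Powers.** The board may unblind any results and make any inquiry it needs (Data and Safety Monitoring). It may also ask for formal analyses of safety data (Safety Data).
- **Event-driven reporting.** Serious or unexpected events are reported to the IRB within 24 hours (Safety and Monitoring). They also go promptly to the IRB, the monitoring committee and, if appropriate, the FDA (section on reporting of unanticipated problems).

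**The concern.** A rule that fires at every 24th subject suggests repeated reviews. In a trial of 24 it fires once, when there is almost nothing left to modify or stop. No other sentence says when cumulative safety data are compiled. The nearest is under Board meeting schedule, "The data to be reviewed by the DSMB will be available to the Board members", which gives no date, cut-off or content.

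The matter at stake is narrow. The expected symptoms are facial flushing and a sensation of the heart pounding, which occurred without a change in heart rate or blood pressure (Rationale for current application). Being expected and non-serious, they need not trigger prompt reporting or an expedited meeting, and vital signs need not reveal them. Staff would hear of them at the visit or in the daily contacts of the following week, but the dosing order is double blind. The board is the body stated to receive safety information unblinded, so it is the one placed to see whether symptoms gather at the largest dose.

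**Working it through.** **1. How often the trigger fires.** Inputs: interval 24 (Safety Data) and planned sample 24 (Sample Size).

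- Packages in total: floor(24/24) = 1.
- Packages before the 24th enrolment: floor(23/24) = 0.
- A second package would need 2 × 24 = 48 enrolled.

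**2. If replaced subjects count as enrolled.** Consent comes before training (Study Visit 1). Subjects with minimal pain at training or failed catheter placement are replaced (Methods and Measures; Volunteer Payment). The documents do not define enrolment or give a replacement rate. Assume that 10% to 40% are replaced:

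- 10%: 24/0.9 = 26.7, so 27 enrolled, and the 24th falls at 24/27 = 89% of enrolment.
- 40%: 24/0.6 = 40 enrolled, and the 24th falls at 24/40 = 60%.

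Either way there is still one package.

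**3. Exposure before that package.** Each subject has 2 dosing visits × 2 infusions = 4, so 24 × 4 = 96 are planned.

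- Upper bound, with no replacements and all 23 earlier subjects finished: 23 × 4 = 92, or 92/96 = 96%.
- If 6 of those 23 are not yet dosed (assumed): 17 × 4 = 68, or 71%.
- If 30 must be enrolled to obtain 24 (assumed, spread evenly, replaced subjects undosed): 4 × 23 × 24/30 = 73.6, or 77%.

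These counts describe the enrolment-triggered package only. They are not counts of infusions given before the board first sees any adverse event data.

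**4. Whether scheduled meetings fill the gap.** Trial duration is not stated. With meetings assumed 6 months apart, the number falling within D months of enrolment is floor(D/6) to ceil(D/6): 0 or 1 for 3 months, 1 for 6, 2 for 12. A short enrolment could fall wholly between two meetings.

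**5. What is expected at the largest dose.** All inputs come from Rationale for current application and Expected outcomes.

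| Regimen | Rate | Modelled concentration | Symptoms |
|---|---|---|---|
| 14 µg over 30 min | 0.47 µg/min | 400 pg/ml | 0 of 10 |
| 7 µg over 10 min (this trial) | 7/10 = 0.7 µg/min | 400 pg/ml | few if any expected |
| 17 µg over 10 min | 17/10 = 1.7 µg/min | not used here | 5 of 8 |

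By rate, the largest infusion is 0.7/0.47 = 1.5 times the event-free regimen and 0.7/1.7 = 0.41 times the regimen with symptoms. By modelled concentration, which is the basis the protocol uses, it equals the event-free regimen.

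**The case against.** The strongest reply is that the board's work is organised around its meetings and not around the enrolment trigger. It issues a summary of serious and unexpected events after each meeting and recommends whether to continue, modify or halt. That output presupposes safety data at each meeting. The board can also call for a by-dose listing whenever it wishes. Serious and unexpected events have their own fast routes, and the symptoms in question were benign by the protocol's account.

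Most of this stands. A reader might infer that the board sees no safety data until the trial is over, or that 96% of infusions go unmonitored. The documents do not support either reading: a scheduled meeting may well see adverse event data, and the 96% is an upper bound for one route only. A reader might also infer from the infusion rates alone that the expectation of few symptoms is unsound. That does not follow, because the event-free regimen was modelled to the same 400 pg/ml.

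The reply does not make the summary certain. The post-meeting report covers serious and unexpected events, the board's powers are discretionary, and no sentence ties compilation of cumulative non-serious events by dose to a meeting. A scheduled meeting might not fall within enrolment at all.

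**Conclusion.** The point holds, at modest severity. The mismatch is exact: an interval of 24 against a sample of 24, with no package before the 24th enrolment. It rests on no assumption beyond the planned sample size. If replaced subjects count as enrolled, the single package comes somewhat earlier, but there is still only one unless enrolment reaches 48. The trigger therefore cannot by itself serve the intermittent recommendations that the monitoring plan describes.

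The consequence is less certain than the mismatch. What is not assured is a cumulative, unblinded, by-dose summary of expected non-serious symptoms before dosing is nearly complete. How late that summary would come depends on trial duration, replacement rate and dosing delay, none of which the documents give. Nothing here shows that the board lacks oversight of serious or unexpected events, or that the planned doses are unsafe.

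**What to change.** Replace the sentence in the Safety Data section with: *Cumulative unblinded safety data, tabulated by dose, will be prepared for every scheduled DSMB meeting.* This is the essential change, and it brings the section into line with Board meeting schedule.

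Because enrolment could finish between two meetings, the sponsor and the board may also add one listing after a number of dosed subjects below 24, which they should choose; the documents give no basis for a particular figure. The count should be of subjects dosed, since a count of consents could produce a listing with few exposures.

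The cost is one sentence and one or two short extra listings for the existing board. There are no extra subjects and no efficacy look, so the dose-response analysis is unaffected.
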